#### 7.3.1.1. Overall Survival and Survival at 12, 18, 24 and 36 months of age

Survival will be analyzed as the proportion of subjects surviving to 12, 18, 24, and 36 months of age. A 95% exact confidence interval, calculated using the Clopper-Pearson method, will also be presented for each proportion estimate. In addition, the Kaplan-Meier estimate of median survival time and 95% confidence interval will be summarized as well as the number of deaths and the number and percentage of subjects censored. Kaplan-Meier curves of survival since birth and survival since first dose of SBC-102 will be presented. Kaplan-Meier estimates of median survival since first dose of SBC-102 will also be provided, along with 95% CIs, if estimable.

Survival rates and median age at death derived from this study will be compared to rates/times reported in the literature and previous studies. No statistical comparisons will be performed.

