3.2.3 Study Duration

The duration of each subject's treatment in the study is expected to be at least 18 months, and subjects may continue to receive treatment in the study for up to up to 3 years. Therefore, the overall duration of a subject's participation in the study, inclusive of a 3-week screening period and a 4-week follow-up period, may be up to 3 years and 7 weeks.

4 Study Population

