4.2 Number of Subjects

In light of the extremely low prevalence of the target disease, up to 10 subjects will be enrolled in the study.

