4.6.2 Procedures for Discontinuation

A subject's parent or legal guardian is free to withdraw consent and/or discontinue the subject's participation in the study at any time, without prejudice to further treatment. A subject's participation in the study may also be discontinued at any time at the discretion of the Investigator or Sponsor.

Should a subject's parent or legal guardian decide to withdraw consent, all efforts will be made to complete and report the observations as thoroughly as possible. The parent or legal guardian of subjects who are discontinued from the study should be asked about the reason(s) for their discontinuation and about the presence of AEs. The date and the reason for discontinuation will be recorded in the eCRF. Subjects who discontinue prior to IMP administration will be replaced.

Subjects who are prematurely withdrawn from the study will be asked to complete all discontinuation assessments prior to withdrawal (see Appendix A), if possible. Information on the survival of discontinued subjects will be collected until completion of the study. Serious AEs will be followed according to Section 7.2.3 and reported according to Section 7.4. A subject will be considered early terminated if the subject does not complete the study after enrollment. A subject will be considered discontinued due to an AE if the subject received any infusion or partial infusion of the investigational medicinal product, but did not complete the study because of an AE, whether or not considered drug related. At the end of the subject's participation in the study, the Investigator will document the reason(s) for study discontinuation in the eCRF.

In the event that a subject dies, permission will be sought (through a separate informed consent form) from the subject's parent or legal guardian for an autopsy. Samples collected from these procedures will be used to further understand LAL Deficiency and the effect of sebelipase alfa.

When a subject fails to return for scheduled assessments, the following efforts should be made to contact his/her parent or legal guardian to determine a reason for the failure to return: 3 attempts, including the date and time, to be documented in the subject's chart. If there is no response, a certified letter should be sent. After these efforts have been exhausted, a subject should be identified as lost to follow-up in the eCRF.

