# 7. STATISTICAL ANALYSIS

The Alexion Biostatistics Department or designee will perform the statistical analysis of the data derived from this trial. The analysis will be performed using the SAS® Life Science Analytics Framework version 4.7.2 or higher.

No formal inferential statistical testing will be performed. As appropriate, 95% two-sided confidence intervals (CIs) will be calculated around the estimates based on the exact binomial distribution (Clopper-Pearson method) for binomial endpoints and the t-distribution for continuous endpoints. Confidence intervals, where presented, will be considered descriptive and will be provided to facilitate clinical review and interpretation.

All data collected in this study will be provided in subject data listings sorted by subject number; the dose of SBC-102 temporally associated with the data will be included on the listing. Summary tables and/or graphs will be presented for each endpoint, as appropriate to the data, by evaluation time point.

Unless otherwise noted, the following standard conventions will be used for creating descriptive summaries:

- Continuous numeric endpoints will be summarized by providing the number of subjects with non-missing data, the mean and standard deviation (SD) of the data, and the minimum, first quartile (Q1), median, third quartile (Q3), and maximum value. Mean, median values, Q1 and Q3 will be presented with one decimal point more than the original value, SD will be displayed with two decimal points more than the original value will have the same number of decimal points as the original value;
- For categorical endpoints, the number and percentage of subjects with each possible outcome will be displayed. The denominator for percentages will include subjects with missing data.

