# 9.3 Sample Size, Power, and Randomization

No formal sample size calculations were performed for this study; the projected enrollment is based on feasibility. Given the rarity of LAL-D, it is not expected that more than 10 patients will be treated.

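### Survival to 24 and 36 months of age is planned as a crude proportion, although children may leave the study alive before those ages and the survival section does not say how they count

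*SAP*

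**What the plan says.** SAP 7.3.1.1 sets the fixed-age survival rates: "Survival will be analyzed as the proportion of subjects surviving to 12, 18, 24, and 36 months of age". It continues: "A 95% exact confidence interval, calculated using the Clopper-Pearson method, will also be presented for each proportion estimate". The same paragraph plans Kaplan-Meier curves from birth and from first dose, medians, and "the number of deaths and the number and percentage of subjects censored". It names no Kaplan-Meier estimate at the four ages. Protocol 8.7 calls the Kaplan-Meier work complementary and lists 12, 18 and 24 months. Protocol 3.2.2.2 allows other ages if the data permit, and the SAP makes 36 months a fixed age.

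On follow-up, Protocol 3.2.3 says: "The duration of each subject's treatment in the study is expected to be at least 18 months", with a maximum of 3 years and a 4-week follow-up period. Protocol 4.6.2 adds: "Information on the survival of discontinued subjects will be collected until completion of the study".

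Three general rules bear on unknown status:
- SAP Section 7 keeps subjects with missing data in the denominator of percentages.
- Protocol 8.1 makes treated subjects the default denominator.
- SAP 7.3.1 says missing data are generally not imputed and refers to Section 9 for exceptions. Section 9 has no rule for vital status. SAP 9.4.2 and 9.4.3 define time to death only for children who die and give no censoring date.

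**The concern.** A binomial proportion with exact limits treats every child in the denominator as having a known outcome. The SAP itself expects censored children, since it counts them in the Kaplan-Meier output. It nevertheless takes its fixed-age rates from a method that has no place for them.

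The vital-status provision narrows the gap but leaves three groups open: children lost to follow-up (which Protocol 4.6.2 foresees), children who finish treatment alive before the age in question, and children who reach that age after the study has closed. Protocol 4.6.1 adds doubt about who counts as discontinued, because it says a subject who withdraws is regarded as having completed.

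Survival is the first-listed secondary objective, and its rates are to be set beside those in the literature and in previous studies. Living children entered as non-survivors would distort that comparison. If the coding were chosen only after the data are seen, the choice itself could move the rate by tens of points.

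**Working it through.** The plan has no calculated figure to reproduce: "No formal sample size calculations were performed for this study; the projected enrollment is based on feasibility".

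**Inputs from the documents.** Number of children n = 10 at most ("up to 10 subjects will be enrolled in the study", Protocol 4.2). Age at first dose a = 0 to 8 months (Protocol 4.4, exclusion 2). Treatment time T = 18 to 36 months, and follow-up 4 weeks (Protocol 3.2.3). Appendix A sets follow-up at 30 days, or 30/30.4375 ≈ 1.0 month.

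**Assumptions.** The documents give no rate of death or early exit, so those below are illustrative.

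**Step 1: how far follow-up reaches.** Age at last planned contact = a + T + 1.0.

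| Treatment (months) | Age at last contact (months) | Reaches 18? | Reaches 24? | Reaches 36? |
|---|---|---|---|---|
| 18 | 19.0 to 27.0 | all | only if a ≥ 5 | none |
| 24 | 25.0 to 33.0 | all | all | none |
| 36 | 37.0 to 45.0 | all | all | all |

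To be seen at 36 months of age, a child needs T ≥ 36 − 1 − a, which is 27 months of treatment if first dosed at 8 months and 35 months if first dosed at birth. At 18 months of age the requirement is T ≥ 17 − a, at most 17 months, so the expected minimum of 18 months covers it. It therefore covers 12 months of age too.

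**Step 2: effect on one data set of 10 children.** Each child of unknown status moves the proportion by 1/10 = 10 points between the two extreme codings.

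| Sequence before the landmark | Kaplan-Meier | Unknown = not surviving | Unknown excluded | Unknown = surviving |
|---|---|---|---|---|
| 2 deaths, no exits | 80.0% | 8/10 = 80.0% | 8/10 = 80.0% | 8/10 = 80.0% |
| 2 deaths, then 2 exits | 80.0% | 6/10 = 60.0% | 6/8 = 75.0% | 8/10 = 80.0% |
| 1 death, 2 exits, 1 death | 9/10 × 6/7 = 77.1% | 6/10 = 60.0% | 6/8 = 75.0% | 8/10 = 80.0% |
| 3 exits, then 2 deaths | 5/7 = 71.4% | 5/10 = 50.0% | 5/7 = 71.4% | 8/10 = 80.0% |

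Clopper-Pearson limits in the second row are 26.2 to 87.8% for 6/10, 34.9 to 96.8% for 6/8 and 44.4 to 97.5% for 8/10.

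**Step 3: average effect.** Let S be true survival to the landmark and q the chance of leaving before it, with exit unrelated to prognosis. Counting unknowns as not surviving gives S(1 − q) on average. For S = 80% and q = 10, 20 and 30%, that is 72, 64 and 56%. A simulation with constant hazard from 3 months of age gives the same values. It also gives 79, 78 and 77% when unknowns are excluded, and 81, 82 and 83% when they count as surviving. For S = 60% the three codings give 54/48/42%, 59/57/55% and 62/64/66%. With q = 0 all three equal S.

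**The case against.** The strongest defence is that little may go wrong in practice. Eighteen months is an expected minimum. With 24 months of treatment every child passes 24 months of age, and with the full 3 years every child passes 36. Vital status is collected after discontinuation while the study is open. Kaplan-Meier curves, censoring counts and by-subject listings are already planned, so with at most 10 children a reader could recover the rate at any age. Survival is secondary to safety, and the analysis is descriptive: "No formal inferential statistical testing will be performed". The coding that the general rules suggest understates survival, so it cannot manufacture a benefit against the literature.

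Most of this stands. It makes the bias conditional and shows that its direction is against the drug. It does not make the planned rate correct when children are of unknown status, and a curve is not a tabulated estimate with an interval. The Kaplan-Meier median cannot stand in for the rate, because it is not estimable while the curve stays above 50%.

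A reader might infer that the fixed-age figures are wrong however unknown children are counted. The documents do not support that. With all statuses known, crude and Kaplan-Meier rates are identical. In the second row of the Step 2 table, counting unknowns as surviving matches Kaplan-Meier, and in the fourth row excluding them does. Excluding them is in any case not the plan's default denominator.

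**Conclusion.** The point holds in conditional form. SAP 7.3.1.1 chooses an estimator for 24 and 36 months of age that needs complete vital status, and the design does not guarantee it. The most exposed age is 36 months. Applied together, the general denominator and missing-data rules would most naturally count a child last seen alive as not surviving, although the survival section does not say so. With n = 10, that costs 10 percentage points for each such child who is in fact alive. Under the assumptions of Step 3, it reports 64% when true survival is 80% and 20% leave early.

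The size depends on how many children leave alive with unknown status, which the documents do not let one predict. It is zero if none do. It would also go too far to read this as a fault in all the survival results: planned exit does not reach 12 or 18 months, so those ages are exposed only to earlier withdrawal or loss to follow-up. The point concerns a secondary, descriptive endpoint, but it should be settled before the final analysis.

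**What to change.** In SAP 7.3.1.1:

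- Tabulate the Kaplan-Meier estimate at 12, 18, 24 and 36 months of age, with a 95% CI (for example log-log) and the number at risk. Use it for the literature comparison at any age where some child's status is unknown.
- Define the censoring date as the last date known alive, for completers as well as discontinued children.
- Show the number of children with known status at each age, and state how unknown status enters any proportion.
- Keep the Clopper-Pearson proportion at ages where every treated child's status is known. This includes landmarks with no deaths, where the log-log interval is undefined and the exact interval is still available.

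The cost is SAP wording and one or two table columns, and intervals at 36 months may be wider. Kaplan-Meier still assumes that exit is unrelated to prognosis, so reasons for exit should be read beside the estimates.

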#### 7.3.1.2. Abdominal Magnetic Resonance or Abdominal Ultrasound

Change and percent change in liver and spleen volume in multiples of normal and fat content will be calculated from Baseline and tabulated for each evaluation time point. Multiples of normal are defined in Section 9.4.10. Change from baseline will only be calculated if the same mode of assessment, MRI or ultrasound, was used at baseline and post-baseline. Data will be summarized for the endpoints as continuous variables.

#### 7.3.1.3. Clinical Laboratory Tests

Observed measurements, changes and percent changes from baseline to each study time point in serum liver biochemical parameters, serum lipids, serum ferritin, hemoglobin levels, and platelet count will be tabulated. Data will be summarized for the endpoints as continuous variables and relative to the laboratory normal range Spaghetti plots (1 line per subject) and mean plots of absolute value, change or percent change in measurements over time may also be created for selected endpoints. Also see Section 7.2.3.

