3.1.1.1 Dose escalation criteria during first 3 months of treatment

During this period, a subject may be considered for dose escalation if he/she meets 2 or more of the following criteria at a dose of 1 mg/kg gw:

- Failure to gain an average of 5 g/kg body weight per day AND the presence of one or more of the following:
 - weight-for-length (WFL) or weight-for-height (WFH) z-score <-2 based on World Health Organization (WHO) child growth standards; and/or
 - length-for-age (LFA) or height-for-age (HFA) z-score <-2 based on WHO child growth standards
 - weight-for-age (WFA) z-score <-2 based on World Health Organization (WHO) child growth standard
- Albumin <3.5 g/dL
- Alanine aminotransferase (ALT) >2x upper limit of normal (ULN)
- Ongoing requirement for blood and/or platelet transfusion

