4.3 Inclusion Criteria

A subject must meet all of the following criteria to be eligible to participate in this study:

- 1. Subject's parent or legal guardian (if applicable) consents to participation in the study.
- 2. Confirmation of documented decreased LAL activity relative to the normal range of the lab performing the assay or a documented result of molecular genetic testing confirming a diagnosis of LAL Deficiency..
- 3. Substantial clinical concerns, in the opinion of Investigator and Sponsor, of rapid disease progression requiring urgent medical intervention including, but not restricted to, the following:
 - a. Marked abdominal distension and hepatomegaly
 - b. Failure to thrive as evidenced by:
 - i. Weight for height is 2 or more SD below the mean for gender and age
 - ii. Weight curve has crossed downward by more than 2 major percentile lines on the WHO growth curves (1st, 3rd, 5th, 10th, 25th, 50th, 75th, 90th, 95th, 97th, 99th) after having previously achieved a stable pattern of growth
 - Disturbance of coagulation (e.g., requirement for FFP; two values of PT >15 sec, or PTT > 40 sec)
 - d. Severe anemia (e.g., requirement for blood transfusion or hemoglobin < 8 g/dL)
 - e. Sibling with rapidly progressive course of LAL Deficiency

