8.13 Missing or Invalid Data

All data will be analyzed as they were collected in the database.

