#### 7.3.1. Handling of Dropouts or Missing Data

All data will be analyzed as they were collected in the database. Missing data in general will not be imputed, any imputation techniques, if applied, are described in Section 9.

Proprietary and Confidential 30

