#### **Transfusion-Free Hemoglobin**

A subject will be considered to have achieved transfusion-free hemoglobin normalization (TFHN) if the subject meets all of the following criteria:

- 1. Has two post-baseline measurements of hemoglobin at least 4 weeks apart that are both above the age-adjusted lower limit of normal (LLN);
- 2. Has no known additional measurements of hemoglobin that are below the age-adjusted LLN during the (minimum) 4-week period; and
- 3. Had no transfusions during the (minimum) 4-week period, and also no transfusions for 2 weeks prior to the first hemoglobin measurement in the (minimum) 4-week period.

If all 3 criteria are met, the subject will be considered to have achieved TFHN on the date of the first hemoglobin assessment in the 4-week period. The proportion of subjects who achieve TFHN will be summarized and, if sufficient data are available, a summary of time to TFHN will be created.

A subject who is transfusion-free beginning at Week 6 will be considered to have maintained transfusion-free normal hemoglobin if:

• regardless of baseline hemoglobin value, the subject has no abnormally low hemoglobin values beginning at Week 8 of the study and continuing for at least 13 weeks (3 months).

The proportion of subjects who have maintained transfusion-free normal hemoglobin will be summarized.

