#### 9.4.8 Definition of Baseline Values and Change from Baseline

#### 9.4.8.1 Baseline

Baseline is defined as the last available assessment prior to the start of the first infusion of sebelipase alpha. If any Baseline laboratory analyte is evaluated at both the local and the central laboratory, then the central laboratory results will be used for analysis.

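### Descriptive hemoglobin and platelet summaries include values drawn soon after a transfusion with no flag, although the same SAP section applies a 2-week washout to transfusion-free hemoglobin normalization

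*SAP*

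**What the plan says.** SAP 7.3.1.3 provides that observed values, changes and percent changes from baseline at each time point in "serum liver biochemical parameters, serum lipids, serum ferritin, hemoglobin levels, and platelet count will be tabulated". SAP 7.2.3 commits to one-line-per-subject plots of actual value, change and percent change for a list that includes hemoglobin and platelets, and allows mean plots. None of these displays carries a transfusion condition.

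The baseline rule in SAP 9.4.8.1 is: "Baseline is defined as the last available assessment prior to the start of the first infusion of sebelipase alpha". On data handling, SAP 7.3.1 says: "All data will be analyzed as they were collected in the database. Missing data in general will not be imputed". Protocol 8.13 agrees: "All data will be analyzed as they were collected in the database".

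The treatment of hemoglobin as a responder outcome differs. Under the Transfusion-Free Hemoglobin heading of SAP 7.3.1.3, TFHN needs a qualifying period without transfusion and "also no transfusions for 2 weeks prior to the first hemoglobin measurement in the (minimum) 4-week period". The maintained-hemoglobin analysis takes infants who are transfusion-free from Week 6 and judges their values from Week 8.

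The protocol expects some infants to be transfused. Its examples of rapid progression in section 4.3 include "Severe anemia (e.g., requirement for blood transfusion or hemoglobin < 8 g/dL" and "Disturbance of coagulation (e.g., requirement for FFP; two values of PT >15 sec, or PTT > 40 sec". Among the escalation criteria in section 3.1.1.1 is "Ongoing requirement for blood and/or platelet transfusion".

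**The concern.** The SAP accepts that a hemoglobin value soon after a transfusion is not evidence of response, and shuts such values out of TFHN. A few lines earlier it lets the same values into baseline and the by-visit summaries with nothing to mark them.

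Hematological parameters are a secondary objective, there is no control arm, and at most 10 infants are expected, so a few transfused values can move a mean. A transfused baseline makes later change look smaller, and a transfused visit value makes it look larger. A reader of the table cannot tell which has happened, or whether the two offset each other.

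Platelets are the more exposed analyte. Platelet transfusion is foreseen in the escalation criteria, but the unflagged summary is the only platelet result planned.

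**Working it through.** The plan states no figure on this point, so there is none to reproduce. The check is mainly textual, with an illustration of size.

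**Step 1: which analyses have a transfusion rule?**

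| Analysis | Where | Transfusion rule |
|---|---|---|
| TFHN | SAP 7.3.1.3; Protocol 8.7 | None during the period of at least 4 weeks, nor in the 2 weeks before it |
| Maintained normal hemoglobin | SAP 7.3.1.3; Protocol 8.7 | Transfusion-free from Week 6, values judged from Week 8 (8 − 6 = 2 weeks) |
| Hemoglobin: observed, change, percent change | SAP 7.3.1.3, 7.2.3 | None |
| Platelets: observed, change, percent change | SAP 7.3.1.3, 7.2.3 | None |
| Baseline for all of these | SAP 9.4.8.1 | None |

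Both responder analyses use a 2-week gap. The SAP also limits change scores to comparable measurements elsewhere: section 7.3.1.2 computes imaging change only when baseline and follow-up used the same modality.

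**Step 2: is exposure foreseeable?** Red cell transfusion and plasma appear among the entry examples, and ongoing blood or platelet transfusion among the escalation criteria. Protocol 3.1 expects infants to be in hospital for the first several weeks, and Appendix A schedules laboratory tests weekly from Week 0 to Week 4. Recently transfused values are therefore plausible at baseline and early on treatment. The documents do not say how many to expect.

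**Step 3: direction and size.** Let k_base and k_post be the numbers of infants with a recently transfused value at baseline and at the visit, r the rise in hemoglobin, and N the number contributing.

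Shift in mean change = r × (k_post − k_base) / N

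Inputs: N = 10, the enrollment ceiling (Protocol 4.2, SAP 9.3). The range r = 1 to 3 g/dL and the counts are assumptions, because the documents give neither.

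| Net difference (k_post − k_base) | r = 1 | r = 3 |
|---|---|---|
| +2 | 1 × 2/10 = +0.2 | 3 × 2/10 = +0.6 |
| +4 | 1 × 4/10 = +0.4 | 3 × 4/10 = +1.2 |
| −2 | −0.2 | −0.6 |
| −4 | −0.4 | −1.2 |
| 0 (for example 3 and 3) | 0 | 0 |

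For a net difference of 2 to 4 infants, the shift is 0.2 to 1.2 g/dL in either direction.

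**Step 4: one infant.** Suppose the untransfused baseline would be 7.5 g/dL (below the 8 g/dL in the entry example) and the later value is 11. The change is 11 − 7.5 = 3.5 g/dL, or 3.5/7.5 = 46.7%. If a transfusion has raised the recorded baseline by 2, to 9.5, the change is 1.5 g/dL, or 1.5/9.5 = 15.8%. Percent change is hit twice, because SAP 9.4.8.3 divides by baseline. This carries into all of that infant's later change scores, but into no other infant's.

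**The case against.** The strongest reply is that the results that matter are already protected. The secondary hemoglobin endpoint in SAP 5.2.1 is transfusion-free normalization, and the maintained-hemoglobin analysis adds a second safeguard. Mean hemoglobin change is not a listed efficacy endpoint, platelets are exploratory (SAP 5.2.2), and nothing is tested. Subject-level plots and dated treatment listings let a careful reader relate values to transfusions by hand. All of this stands, and it limits the point to supportive description. It does not help a reader of the mean tables, and it leaves platelets with no transfusion-free result.

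A second reply is that dropping flagged values brings its own bias: the infants removed are probably the sicker ones, from 10 at most. Screening lasts no more than 21 days, so an infant whose only pre-dose values are flagged would lose every change score. This also stands, and is why the all-values table should be kept.

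Three stronger readings are tempting but unsupported:

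- A reader might infer that the liver results, including AST and ALT, also measure transfusion. Neither document says that transfusion alters these enzymes.
- A reader might infer that every visit mean is affected. An observed mean is touched only where someone was recently transfused, and a transfused baseline touches only that infant's change scores.
- A reader might infer that infants enter because they need transfusion. Transfusion and plasma sit within two of five non-exhaustive examples, and each of those two can be met on laboratory values alone.

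**Conclusion.** The point holds for the descriptive hemoglobin and platelet summaries. They take recently transfused values as collected, at baseline and at visits, while the same SAP section treats such hemoglobin values as unfit for judging response. Mean change cannot be read as a drug effect at visits where infants were recently transfused, or for infants whose baseline was. TFHN and the maintained-hemoglobin analysis are unaffected as the SAP defines them.

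The protocol synopsis describes TFHN among infants with abnormal baseline hemoglobin, so a reader might infer that a transfused baseline changes its denominator. Protocol 8.7 and the SAP state no such restriction.

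The 0.2 to 1.2 g/dL range is illustrative. It rests on an assumed rise of 1 to 3 g/dL, a net difference of 2 to 4 infants, and all 10 contributing; the bias could be zero. No comparable figure can be given for platelets. All analyses are descriptive, so no error rate or sample size changes. This is a change that should be made, but it is not critical to the trial's conclusions.

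**What to change.** In SAP 7.3.1.3 and 9.4.8.1:

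1. Flag each hemoglobin value drawn within 2 weeks after a red cell transfusion, which is the SAP's own TFHN window.
2. Flag each platelet value drawn within a stated window after a platelet transfusion. The documents give no such window, so it must be fixed before analysis.
3. Keep the all-values summaries. Beside them, show the same summaries without flagged values, applying the exclusion to baseline as well as visits.
4. Report the number of infants recently transfused at baseline and at each visit.
5. Mark transfusion dates on the spaghetti plots in SAP 7.2.3.

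The cost is SAP wording, two derived flags and one extra set of columns. TFHN already needs on-treatment transfusion dates, and Protocol 4.5 has the type of each treatment recorded, which should separate red cells from platelets. One item needs checking. Protocol 4.5 starts that recording at consent, while a 2-week look-back from baseline can reach earlier, so the team should confirm that pre-consent transfusions are captured.

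The downside is a smaller table without flagged values, probably missing the sicker infants. It should therefore stand alongside the all-values table and not replace it.
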